	Sample Size, assuming 30% attrition, 10% refusal	Design Effect (2.5) and Cluster Size Adjusted Sample Size Per Arm	Sample size per arm (80% Public, 20% Private)	Total per Country (2 arms)
Kenya Public	721	2254	1803	4508
Kenya Private			451	
Indonesia Public	686	2144	1715	4288
Indonesia Private			429	

Table 5: Sample Size Calculations, Postabortion

Study Arm	Base sample size of post-abortion clients (per arm – assuming 50% uptake and 40% continuation at 6-months)	Attrition Adjusted Sample Size per arm (estimating 20% attrition)
Kenya Intervention	194	243
Indonesia Intervention	194	243
Total		486

Separate sample sizes have been calculated for Indonesia and Kenya. Estimates aim to measure a difference in the six-month postpartum acceptance of long-acting reversible and permanent methods (LARC+PMs) by postpartum women seeking services at comparison and intervention facilities. Sample size calculations for both countries are based on a 95% two-sided confidence interval with 80% power. The sample size was calculated in two stages. First, we calculated the sample size for simple random sampling. Next, the sample size was adjusted to take into account a design effect of 2.5 in order to adjust for within-cluster correlation and non-response.

In Indonesia, we used an analysis of PPPF utilization from the 2012 Demographic and Health Survey (DHS) and conversations with the My Choice project team (My Choice is a Bill and Melinda Gates Foundation-supported project currently strengthening family planning services at facilities in Indonesia) to estimate a baseline LARC+PM use of approximately 10% at six months postpartum. In Kenya, we analyzed FP method use among a subset of 3,857 women with a child under one year interviewed during the 2014 Kenya DHS to estimate a LARC+PM use rate of 6% at six months postpartum. Sample sizes were calculated to measure a change from 10% to 15% in Indonesia and from 6% to 10% in Kenya at intervention facilities over the course of the study. We have further estimated a need for 20% of the sample to be recruited from private facilities in order to effectively measure changes in both types of facilities. An overview of the sample size for each country is shown in Table 4. This table displays the required number of post-pregnancy women to be recruited per arm to measure the change in LARC+PM use post-pregnancy from 10% to 15% in Indonesia and from 6% to 10% in Kenya at the end of the study.

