Once identified, the study managers will contact the potential key informants and introduce the study using the prepared recruitment script. If they are interested in participating, a date and time for the interview will be finalized. KIIs will be conducted at both baseline and endline of the study period.

Client Interviews, Focus Group Discussions, and Postabortion In-Depth Interviews:

Client Interviews: After receiving permission from the facility to implement the study there, RAs will be placed at each facility to recruit and interview clients. Initial recruitment will be done by ANC, maternity ward and postabortion care providers using the provided recruitment scripts. The study design as related to patient recruitment will differ slightly between Kenya and Indonesia for the following reason: During an assessment completed in April of 2016, we determined that while the majority of Kenyan ANC patients attend the same facility for their antenatal care (ANC) visits and their Labor and Delivery (L&D) visits, Indonesian patients are less likely to do so [8]. In order to reduce higher than optimal loss to follow-up between an ANC and L&D, we will be recruiting postpartum women in Indonesia at their delivery visit. However, as we will not be comparing Kenyan outcomes to Indonesian outcomes, we will recruit Kenyan pregnant women at their ANC visits for the postpartum aspect of the study. Recruitment of postabortion women will take place prior to discharge after receipt of treatment for a miscarriage or incomplete abortion at study facilities in both countries.

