After being identified by providers through use of standardized screening tool, a document for providers that presents the study eligibility criteria and the study introduction script, providers trained in use of the study introduction script will explain the study and ask clients if they are interested in participating in the study. If they are, the providers will direct the RAs to the clients. If the client is not in a private room, the RAs will then bring the clients to a private location. When they are in a private area, the RAs will provide more detailed information about the study through use of a recruitment script. RAs will determine clients' study eligibility, using the RA's screening tool which screens for the inclusion criteria discussed above, and will ensure that clients provide full informed consent to participate. Upon meeting these criteria and providing informed consent, clients will begin the process for study enrolment. The first step in study enrolment is the provision of the participant's contact information. If the participant refuses to provide any contact information, her basic demographic information will be recorded but she will not continue with study enrolment. If she does provide her contact information, she will be enrolled in the study. If the participant does not meet study eligibility criteria or is not willing to provide informed consent, she will be thanked for her time and the interview will stop.

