Client Interviews: Clients opting to participate in this study will be contacted two to three times for the interviewer-administered survey

As displayed in **Table 1** and **Figure 1**, the point of recruitment or entry into the study will differ by country and type of client.

[figure not shown]

Figure 1: Client Participation timepoints

For Postpartum Women

ANC: In Kenya, the first contact for pregnant/postpartum participants, will take place at the participant's ANC visit. At this time, a 30 minute questionnaire will be administered which includes sociodemographic information, assessment of the quality of the client provider knowledge attitudes and beliefs regarding PPFP, and barriers and facilitators of intended PPFP use. The interviewer will also ask to see their ANC card and Mother Child Booklets and note

any pertinent medical or gynecological history that might be relevant to the study – this includes chronic diseases like hypertension, diabetes, HIV and tuberculosis.

Immediate Postpartum: The **first contact for Indonesian postpartum clients** and the **second contact for the Kenyan Postpartum client** will be during the immediate postpartum period, within 72 hours of delivery in Indonesia, within 48 hours of delivery in Kenya. The questionnaire in both countries will be administered to determine whether or not the client received a modern FP method after delivery, how the participant feels about the FP services offered to them during labor and delivery, the participant's knowledge, attitudes and beliefs about PPFP, and reasons for choosing the FP method they chose or for not accepting a FP method at that time. The Kenyan visit will take about 30 minutes while the Indonesian visit will take about 45 minutes. In Indonesian, supplementary questions will be used to collect similar information to what was collected during ANC in Kenya. These questions will identify sociodemographic information and assess the client's perceptions of the quality of the provider interaction at ANC. The interviewer will also ask to see their ANC card and Mother Child Booklets and note any pertinent medical or gynecological history that might be relevant to the study.

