XII. Please complete the attached worksheet of your Logic Model and submit to Jhpiego IRBhelp with your completed research protocol. *This is for Jhpiego internal review only.*

COMPLETE THE FOLLOWING SECTIONS WHEN RELEVANT TO YOUR STUDY:

XIII. Secondary Data Analysis of Existing Data:

A. Study Design:

1. Describe your study design and methods. The study design must relate to your stated aims/objectives.

In addition to the methods described above, the study will monitor immediate postpregnancy family planning clients and participating providers and facilities through analysis of routine program and facility records. These records are outlined below.

FP Facility Register	Facility clients	Determine overall facility PPFP acceptance, PPFP method mix and adverse events	Monthly service statistic record review	Descriptive statistics
Supportive Supervision Records	Kenya: Intervention Site Providers Indonesia: All providers	Measure service quality against PPFP performance standards	Intervention Area: Kenya: 3 and 12 months post-training Indonesia: Beginning of the study, Year 2, Year 3 Control Area: Kenya and Indonesia: month 30	Descriptive, chi-sq, ANOVA (depending on sample size)

Family Planning Facility Registers: Information about immediate PPFP clients will be documented in a Family Planning register at the intervention and control health facility where they receive care – part of the health system. This information will be used to track overall PPFP service statistics, assist with validating responses from the Client Interviews, and help the study team ensure that the Client Interview sample continues to be representative of the overall client population (especially regarding adolescent enrollment).

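### Indonesia: arm-aware providers make the first approach after delivery, with no stated rule that every eligible woman is introduced and no planned check of enrolled women against register uptake by arm

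*Protocol*

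**What the plan says.** Protocol section V.A.1 (Recruitment Process, Client Interviews) gives the first approach to facility staff: "Initial recruitment will be done by ANC, maternity ward and postabortion care providers using the provided recruitment scripts". Providers identify women with a standardized screening tool that sets out the eligibility criteria, read an introduction script and ask about interest. If the woman is interested, "the providers will direct the RAs to the clients". Section V.B.1.c adds that providers screen on demographic and pregnancy-related criteria and that research assistants (RAs) confirm eligibility of the women referred to them.

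The timing differs by country. Kenyan postpartum participants are recruited at ANC. Indonesian ones are recruited at the delivery visit, within 72 hours and before discharge. Section V.C.1 (Immediate Postpartum) says the questionnaire at that first Indonesian contact is used "to determine whether or not the client received a modern FP method after delivery".

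Section V.C.5 assigns the package by area. Intervention facilities are trained and supported throughout data collection, and control facilities receive the package afterwards. The blinding item is answered N/A.

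Section III.B sizes the study on six-month LARC+PM acceptance "by postpartum women seeking services at comparison and intervention facilities". Section XIII.A.1 says the family planning registers, kept at intervention and control facilities, will "help the study team ensure that the Client Interview sample continues to be representative of the overall client population", with adolescent enrolment singled out. SAP section C follows labour and delivery totals and acceptors by method type. SAP section A compares acceptance between arms by logistic regression. The SAP contains no comparison of enrolled with non-enrolled women and no sensitivity analysis for selection.

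**The concern.** The person who decides whether a woman hears about the study knows the facility's arm and, in Indonesia, may know whether she has already taken a method. A method received before discharge bears on the six-month outcome. If introduction to the study depends on method received, and does so differently in the two arms, enrolled women misrepresent uptake by different amounts in each arm. The between-arm difference then mixes programme effect with referral practice. A larger sample does not remove this. Covariate adjustment does not either, unless it captures what drove referral.

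RAs see only referred women, so no step described in the documents would reveal who was passed over. The protocol uses a random draw elsewhere: focus group participants are contacted at random from a list (section V.A.1). The main client sample has no stated consecutive or random rule.

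**Working it through.** **1. The plan's own figure.** Section III.B: "Sample size calculations for both countries are based on a 95% two-sided confidence interval with 80% power", and "Sample sizes were calculated to measure a change from 10% to 15% in Indonesia and from 6% to 10% in Kenya". The pooled two-proportion formula for Indonesia is

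n = [1.96·√(2·0.125·0.875) + 0.842·√(0.10·0.90 + 0.15·0.85)]² / 0.05² = 686 per arm,

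which matches Table 4 (Kenya likewise gives 721). The final 2144 per arm equals 686 × 2.5 / 0.8. The planned Indonesian effect is therefore 5 points.

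**2. Size of a possible selection bias.** The documents give no referral rates, so these are assumed over a range. Let p = 10% be true six-month use in both arms. Let s be the share of six-month users who already had the method at referral. Let R be how many times as likely those women are to be referred as all others, in the intervention arm only. For simplicity, women given a method before discharge are taken to be still using it at six months. With a = s·p, the rate seen in the intervention arm is

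q = [p + a(R − 1)] / [1 + a(R − 1)].

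| R | s = 1 | s = 0.5 |
|---|---|---|
| 1.1 | 0.110/1.010 = 10.9% | 0.105/1.005 = 10.4% |
| 1.25 | 0.125/1.025 = 12.2% | 0.1125/1.0125 = 11.1% |
| 1.5 | 0.150/1.050 = 14.3% | 0.125/1.025 = 12.2% |

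The control arm would show 10% throughout, so the spurious difference runs from 0.4 to 4.3 points. With s = 1, producing the whole planned 5 points needs R = (0.15/0.85)/(0.10/0.90) = 1.59.

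**3. Chance of a false positive.** Take 2144 per arm, the 30% attrition in the Table 4 label and the plan's design effect ("the sample size was adjusted to take into account a design effect of 2.5"). The effective size is 2144 × 0.7 / 2.5 ≈ 600 per arm. With no true effect, the chance of a significant result favouring the intervention is about 23% when 12.2% is seen against 10%, and about 62% when 14.3% is seen against 10%.

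**4. Room for selection.** Indonesia has 4 facilities per arm (section III.B) and recruits over about 18 months (months 6 to 24, Appendix II): 2144 / 4 / 18 = 29.8 women per facility per month. If a fraction f of deliveries is enrolled, q cannot exceed p/f, reached when every acceptor is enrolled.

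- At the section III.B entry minimum of 50 deliveries a month, f = 29.8/50 = 60%, so q could reach 0.10/0.596 = 16.8%. All the ratios above are possible.
- At the average of 30 deliveries a month in section XIII.A.2, f = 29.8/30 = 99%, so q could not exceed 0.10/0.993 = 10.1%. Almost no selection is possible.

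The figure of 50 is a floor for study facilities. The figure of 30 is an average over 62 project facilities. The two need reconciling before the room for selection can be judged. Busier sites leave more room.

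**The case against.** Providers do not choose freely. They work from a standardized tool and a fixed script, on criteria that do not include contraceptive status. Training covers sampling procedures (section X.A), and a field manual and SOPs are to be written (section X.B). A consecutive rule may exist there, so its absence can be stated only for the protocol and SAP. This stands as a limit on the point. It does not close it, because a tool that defines eligibility does not oblige anyone to introduce every eligible woman.

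The register check is a real safeguard. It covers both arms, and the registers record acceptance and method mix independently of enrolment, so an excess of acceptors among enrolled women could in principle be seen. What is missing is a stated comparison by arm and a stated response.

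No provider or facility is paid (section IX.A), and individual quality results are not shared with facilities (section VII.C). Nothing shows that intervention providers would favour acceptors while control providers would not. Equal selection in both arms would largely cancel, and the direction could even reverse.

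A reader might infer that the recruitment procedure will produce a false effect of some 4 points, close to the planned 5. The documents do not support that. It needs a referral ratio near 1.5 in one arm only, every six-month user already holding the method at referral, and enough deliveries to leave providers a choice. No document gives any of these.

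A reader might also extend the point to the whole study. Kenyan postpartum women are recruited before delivery, so selection there could act only through intention or interest. The postabortion sample is sized for the intervention arm only, so selection there would affect a proportion and not a between-arm contrast.

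**Conclusion.** The point holds for Indonesia as an unguarded route to bias, not as a demonstrated one. Arm-aware providers make the first approach after delivery, a method may already have been given, and neither document states a consecutive rule or a check of enrolled women against register uptake by method and arm.

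Under referral ratios of 1.1 to 1.5 in the intervention arm only and 10% true use in both arms, the apparent rate runs from 10.9% to 14.3% if all six-month users had the method at referral, and from 10.4% to 12.2% if half did. All ratios and shares are assumptions. The possible bias is negligible if facilities average about 30 deliveries a month and substantial at 50 or more. This is worth fixing because the remedy is cheap and selection that is never recorded cannot be properly assessed afterwards.

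**What to change.** In Protocol section V.A.1, state that for Indonesia the on-site RAs work through eligible deliveries consecutively and ask the provider to introduce each woman in turn. This keeps the provider introduction. Keep only a de-identified or aggregate tally, by facility, of eligible women not introduced or refusing. Individual records on women who have not consented would raise a consent question, since section V.B.1.f seeks no waiver. The tally should therefore be subject to IRB approval.

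In the SAP, prespecify a comparison by facility and arm of LARC+PM at discharge among enrolled women with the register totals already planned in section C (labour and delivery clients, and acceptors by method). State how a discrepancy will be handled. Note that the registers include women who were not eligible (Protocol section XIII.B.1), so exact agreement is not expected. Add one sensitivity analysis of the six-month contrast that weights enrolled women to the register's discharge-method distribution.

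The cost is a little RA time, a possible amendment that must wait for the relevant IRBs (section XVI.D), and one extra analysis. RAs and registers are already in the plan.

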Table 6: Schedule of data collection by category of respondents

Participant Data Collection	Purpose		Version of tool by category of respondent	Time Points	Duration of data collection
Key Informant interviews	Determine contexts related to facilitators and barriers to ANC and post-pregnancy women accessing PPFP counseling and service provision	1	Ministry of Health/Policymakers	2 times (beginning of study [approx. month 4–6], end of study [approx. month 30–36])	90 minutes per session
		2	Community Influencers	2 times (beginning of study [approx. month 4–6], end of study [approx. month 30–36])	90 minutes per session
		3	Public facilities (providers and management)	2 times (beginning of study [approx. month 4–6], end of study [approx. month 30–36])	90 minutes per session
		4	Private facilities (providers and management)	2 times (formative assessment, end of study [month 30–36])	90 minutes per session
Client Interviews	Understand relationships between client satisfaction, attitudes related to social contexts and services provided, PPFP knowledge and FP intentions, use and continuation	1	ANC Interview (#0) (Kenya only)	ANC (> 28 weeks gestational age)	30 to 45 minutes
		2	Immediate Pre-discharge Interviews (#1)	Immediately following pregnancy (within 48 hours)	30 to 45 minutes
		3	Six-month Interviews (#2)	6 months post-pregnancy	30 to 45 minutes
	To gain qualitative data to identify social,	1	Public Facility Acceptors (adult)	(midpoint of study) When client is 6 to 12 months post-pregnancy	90 minutes

Focus group discussions	cultural, contextual, and service-, age- and gender-related factors affecting women's perceptions of, access to and use of FP	2	Private Facility Acceptors (adult)	(midpoint of study) When client is 6 to 12 months post-pregnancy	90 minutes
		3	Public Facility Acceptors (adolescent)	(midpoint of study) When client is 6 to 12 months post-pregnancy	90 minutes
		4	Private Facility Acceptors (adolescent)	(midpoint of study) When client is 6 to 12 months post-pregnancy	90 minutes
		5	Public Facility Non-Acceptors	(midpoint of study) When client is 6 to 12 months post-pregnancy	90 minutes
		6	Private Facility Non-Acceptors	(midpoint of study) When client is 6 to 12 months post-pregnancy	90 minutes
In-Depth Interviews (IDIs)	Gain qualitative data to identify the social, cultural, contextual, economic and service-, age- and gender-related reasons women did not receive an immediate post-abortion family planning method	1	Postabortion non-acceptor In-Depth Interviews	6 months postabortion	90 minutes

3. Describe the expected duration of the study from the perspective of the individual participant and duration overall.

The Key Informant Interviews for MOH officials/policymakers, community influencers and facility management and providers will take place at the beginning of the study period (prior to implementation of the intervention) and at the end of the study period (immediately following completion of data collection).

The duration of the study from the perspective of the Kenyan postpartum clients will be from a minimum of 7 months to a maximum of 13 months, while duration of the study from the perspective of the Indonesian postpartum clients will be from a minimum of 6 months to a maximum of 12 months postpartum. All Kenyan clients will be interviewed at ANC (28 weeks gestation and later), immediately postpartum, and 6 months following. All Indonesian clients will be interviewed at their immediate postpartum period and 6 months following. Some postpartum clients between 6 and 12 months postpartum in both countries will be asked to take part in a focus group discussion.

The duration of the study from the perspective of all postabortion clients will be 6 months. Clients will be interviewed at the immediate postabortion period and again 6 months later. Some of the postabortion clients will take part in an IDI, which will also take place 6 months following the postabortion period. The time spent actually collecting data varies by the tool used; table 7 summarizes the data collection time burden for the study participants – last column.

4. Provide a brief data analysis plan and a description of variables to be derived.

Key Informant interviews, Focus Group Discussions and In-Depth Interviews: *Data analysis:* Key informant interviews, Focus Group Discussions and In-Depth Interviews will all be analyzed using Grounded Theory methods. Initial KII, FGD and IDI responses will be translated, transcribed, coded, and analyzed using software to facilitate data management. Quality of translation will be checked for each (KII, FGDs and IDIs) through back translation of a randomly-selected subset of 6 interviews. Using analytical software, coding will be used to conceptually name the data and reduce it to manageable units of information that cover broad and general categories. *A priori* codes will be developed based on the concepts of interest in this research (perception of risk, benefits and beliefs, etc.) and the study aims. As additional KII, FGDs and IDIs are conducted, these *a priori* codes will be complemented by additional codes that reflect themes and concepts that emerge from the data. Codebooks will be developed for the different concepts to facilitate consistency in the coding process. The coded data will be organized into a hierarchy of themes which are then meaningfully linked to each other to show patterns, relationships and explanations. In conjunction with the coding process, memos will be used

to develop conceptual categories and themes and to track emerging insights and interpretations [11]. Qualitative research software such as QSR NVivo or ATLAS.ti will be used to analyze the data.

Client Interviews: Data Analysis: After data have been thoroughly cleaned, the study team will report on all outcomes included in the study tools as well as the service statistics collected as part of this study (see Section XI). The team will calculate the proportion of pregnant/postpartum women who choose a FP method during antenatal care (ANC) or early labor, and, of those, what proportion received the FP method in the immediate postpregnancy period (prior to discharge). Regression models may be used to explore differences in acceptance of PPFP between the intervention and control facilities, different demographic groups, or to compare acceptance among clients receiving varying levels of care (as determined through facility and performance assessments). Select data from the client interviews will be combined with key facility level indicators for a multilevel analysis of the factors affecting intention to use and receipt of PPFP.

Facility Audits: Data Analysis: Mapping of facilities will be visually analyzed to provide further understanding of structural issues that may influence perceptions and key behaviors. We will also utilize multi-level data analysis to explore the feasibility of IPPI using STATA. Select data from the client interviews will be combined with key facility level indicators for a multilevel analysis of the factors affecting intention to use and receipt of immediate post-pregnancy family planning methods.

[figure not shown]
Furthermore, triangulation across methods will help to ensure quality of study findings and offer opportunities for deeper insights into the study concepts [12]. Observations will also be collated with qualitative analysis results and used to strengthen themes identified through key informant data. In addition, a team approach to data analysis will be employed where different researchers provide feedback on emerging interpretations and analysis and check developing categories and concepts back against the original data. In this way, an “audit trail” will be used to help ensure trustworthiness of findings and gather input from multiple investigators [12].

5. Answer the following if they are relevant to your study design:

A. If the study has different arms, explain the process for assigning participants (intervention/control, case/control), including the sequence and timing of the assignment.

The study will employ a quasi-experimental mixed-method design; both quantitative and qualitative data will be collected at multiple time points. In coordination with the MOH, we will first identify an “intervention area” and a “control area” at County-level in Kenya and an “intervention area” and a “control area” at District-level in Indonesia. Within the “intervention areas,” we will identify intervention facility sites (six in Kenya and four in Indonesia) and match them with an equal number of control facility sites from the “control areas,” based on a list of predetermined criteria (e.g., service statistics and client demographics).

All facilities in the “intervention area” will receive all facility level training and support interventions at the beginning of and throughout the study data collection period, while all facilities in the “control area” will be afforded the benefits of the interventions in a phased manner; in the last 6 months of the study timeline, after data collection activities are completed. This is demonstrated in the following graphic:

*Note: exact number of implementation sites TBD

- B. If human biospecimens (blood, urine, saliva, etc.) will be collected, provide details about who will collect the specimen, the volume (ml) and frequency of collection, how the specimen will be used, stored, identified, and disposed of when the study is over. If specimens will be collected for use in future research (beyond this study), complete the "Biospecimen Repository" section below.
N/A
- C. If genetic/genomic analyses are planned, address whether the data will be contributed to a GWAS or other large dataset. Address returning unanticipated incidental genetic findings to study participants.
N/A
- D. If clinical or laboratory work will be performed at JHU/JHH, provide the JH Biosafety Registration Number.
N/A
- E. If you will perform investigational or standard diagnostic laboratory tests using human samples or data, clarify whether the tests are validated and/or the lab is certified (for example is CLIA certified in the U.S.). Explain the failure rate and under what circumstances you will repeat a test. For all human testing (biomedical, psychological, educational, etc.), clarify your plans for reporting test results to participants and/or to their families or clinicians. Address returning unanticipated incidental findings to study participants.
N/A
- F. If your study involves medical, pharmaceutical or other therapeutic intervention, provide the following information:
 - a. Will the study staff be blind to participant intervention status?
N/A

- b. Will participants receive standard care or have current therapy stopped?
N/A
- c. Will you use a placebo or non-treatment group, and is that justifiable?
N/A
- d. Explain when you may remove a participant from the study.
N/A
- e. What happens to participants on study intervention when the study ends?
N/A
- f. Describe the process for referring participants to care outside the study, if needed.
N/A

VI. Data Security and Confidentiality Protections:

A. Personally Identifiable Information (PII):

Please identify the Personally Identifiable Information (PII) that you may be collecting and using at any of the following stages of your study: ***Recruitment, Consent, and Study Implementation.***

Name, signature, initials, or other identifiable code	
Geographic identifier: address, GPS location, etc.	
Dates: birth, death, clinical service, discharge, etc.	
Contact information: phone numbers, email address, etc.	
ID: Social Security Number, driver's license number, etc.	
Health record identifiers: medical record, insurance plan number, etc.	
Account numbers	
Device identifiers: e.g., implants	
Internet identifiers: IP address, social media accounts	
Biometric identifiers, including finger and voice prints	
Audio recordings	
Video or full face photographic images	
Genomic/genetic data	
Any other unique identifying number, characteristic, or code (note: this does not mean the unique code assigned by the investigator to code the data)	
Other: Click here to enter text.	

B. Recruitment:

Will you collect identifiers for the purpose of contacting potential participants? Yes No

If yes, will you retain the identifiers after the recruitment contact has been made? Yes No

C. Data Collection:

In what form will you collect and store PII? When you respond, think of PII collected for recruitment, consent, and other study purposes.

1. **Hard Copy/Paper:** Yes No

If yes, please answer the following:

a. How will the data be kept secure during transfer from study collection site to storage site?

Depending on the setting, we will be using a combination of paper and tablets. Consent may be collected via paper consent forms with either a signature, initial or the participant's mark in the signature line next to the participant's printed name. While all efforts will be made to ensure that all other study data is collected in a REDCap tablet based system, interviews may be collected on paper tools if issues arise with the REDCap tablet based data collection system. All paper-based forms will be transferred in a secured box or briefcase to the regional study offices by the data collection officer daily.

b. Will the data be secured in a locked cabinet or room? Yes No

c. Are the data collection forms and study data stored without personal identifiers and separate from the study IDs/code? Yes No

d. How long after study completion will you keep the hard copy/paper forms?

The paper forms will be destroyed five years following completion of study activities.

2. **Electronic:** Yes No

If yes, please answer the following:

a. Will the data be collected/stored on a portable device (laptop, mobile phone, tablet, PDA) protected by encryption? Yes No

b. Will the data be stored on a secure server or in the Cloud/Web?

Secure Server Cloud/ Web

c. Will it be encrypted? Yes No

d. Will you be backing up your data? Yes No

3. **Audiotape:** Yes No

If yes, please answer the following:

a. Will you store the audiotape securely in a locked cabinet/room until transcription is complete? Yes No

b. Will the audiotape be destroyed after transcription? Yes No

If no, why not?

4. **Photograph/Video:** Yes No

If yes, please answer the following:

- a. Will the photographs/videos be stored securely in a locked cabinet or room? Yes No
- b. Will the photograph/video be destroyed? Yes No

If yes, when?

D. PII De-Identification of Data Used for this Study:

When will you destroy the PII and/or the code linking the PII with the study ID?

All paper-based and electronic study forms will be destroyed five years following completion of the study.

Audio recordings of Key Informant Interviews, Focus Group Discussions and In-Depth Interviews will be transcribed and destroyed immediately upon transcription. The transcriptions will not have identifiers.

E. Data Storage and Analysis:

One of the keys to protecting PII is the proper use of tools to share and conduct your analysis. JH and JHSPH offers several options for you to consider. Please select the system that you plan to use to protect your study data by clicking the box. Consult JHSPH IT for assistance if needed.

- JH Virtual Desktop:** IT@JH provides (for a monthly fee) a virtual Windows desktop.
- JHSPH SharePoint and File Shares:** These systems provide a managed and secure platform for your research project. They also provide a built-in encrypted backup solution.
- JHSPH RedCAP or HPCC:** These are departmentally managed applications.
- JHBox:** Johns Hopkins Box (JHBox) is a secure cloud-based file sharing and file storage service.
- Independent Departmental Servers and Systems:** These servers are typically managed by departmental or research team IT staff.
- Other:** Please provide details regarding any other systems being utilized.

F. Other Data Security Measures:

In addition to the details regarding data collection, please review the following questions. This additional information will be utilized to assist in the development of a comprehensive Data Security plan. This would include the systems used to analyze the data, data security contacts and additional requirements.

1. Do you have a designated person on your research team who is the technical contact for a Data Security plan? Yes No

If yes, please provide a contact name:

2. Does your sponsor have other specific data security requirements for the study data? Yes No

If possible, please explain:

The Bill and Melinda Gates Foundation has a presumption in favor of disclosure with respect to information concerning our activities subject to operational and practical considerations and absent the following circumstances:

- Security and safety: disclosure poses a risk of physical harm to persons or property.
- Personal information: disclosure intrudes on personal privacy or breaches confidentiality.
- Legally privileged and commercially sensitive information: disclosure violates legal commitments, such as non-disclosure agreements and confidentiality agreements, or would result in substantial harm to our grantees, partners or suppliers.
- Timing of publication: disclosure upsets a dynamic process in ways that pose substantial risk to achieving the outcomes sought by our grantees and partners.
- Premature documents: document is too early in development to publish.
- Deliberations: Information related to our own internal deliberations and communications and deliberations and/or negotiations with third parties.

3. Please add any other information that you believe is relevant to data security.

G. Certificate of Confidentiality:

Will the study data stored in the **United States** be protected by a Certificate of Confidentiality?

No

If yes, explain who will apply for and maintain the Certificate. N/A

(http://grants.nih.gov/grants/policy/coc/appl_extramural.htm)

H. Will you use clinical data of 500 records or more from Johns Hopkins Hospital and its affiliates?

Yes No

If yes, please complete the JHM Data Security Checklist available on the JHSPH IRB website:

www.jhspph.edu/irb and upload a copy of the checklist to the “Miscellaneous” section.

VII. Risks of the Study:

A. Describe the risks, discomforts, and inconveniences associated with the study and its procedures, including physical, psychological, emotional, social, legal, or economic risks, and the risk of a breach of confidentiality. These risks should be described in the consent documents.

Clients: The main risk to participants is loss of confidentiality. There is also a minor risk that some questions may make participants uncomfortable. Participants will be told during the consent process that they may skip any questions that they do not wish to answer and they may stop the interview at any time without any consequences.

Providers and Facility Managers: The risk to service providers for participating in this study is minimal and relates to any potential damage to their professional reputation if it is discovered that a service provider is not performing his/her job correctly.

Policy Makers and Community Influencers: There are no anticipated risks to community influencers for participating in the study. However, some individuals may feel uncomfortable answering questions about family planning and/or reproductive health.

B. Describe the anticipated frequency and severity of the harms associated with the risks identified above; for example, if you are performing “x” test/assessment, or dispensing “y” drug, how often do you expect an “anticipated” adverse reaction to occur in a study participant, and how severe do you expect that reaction to be?

We do not anticipate adverse events to occur as a result of participation in the study.

